10.3. Contraindications to Vaccination

The following events constitute a contraindication to vaccination at that point in time:

- Severe acute illness at the time of vaccination.
- Fever (body temperature $\geq 38.0^{\circ}\text{C}$) at the time of vaccination.

If any of these events occur at the scheduled time for administration of study vaccine on Day 1, enrollment at a later date is permitted at the discretion of the investigator and after discussion with the sponsor. In case of occurrence at the time of revaccination, revaccination at a later date is permitted under the same conditions.

11. STATISTICAL METHODS

Statistical analysis will be done by the sponsor or under the authority of the sponsor. A general description of the statistical methods to be used to analyze the efficacy and safety data is outlined below. Specific details will be provided in the Statistical Analysis Plan.

In the following sections, the following terminology is used to describe the different analyses of the primary efficacy endpoints of the study:

An interim analysis (IA) is any analysis performed by the IDMC before the primary analysis. The outcome of an IA can be any of the following:

- “superiority”: proof of concept is reached, there is statistically significant proof that the active study vaccine prevents more RT-PCR-confirmed RSV-mediated LRTD compared to placebo (for at least one case definition),
- “futility”: it is unlikely that continuing the study will result in statistically significant proof that the active study vaccine prevents more RT-PCR-confirmed RSV-mediated LRTD compared to placebo (for all case definitions),
- “continue”: neither superiority nor futility is shown and the study should continue as planned.

The sponsor will remain blinded to the actual results of any IA and will only receive the outcome as described above from the IDMC. Interim analysis can occur at the end of the RSV season (if the required number of RT-PCR-confirmed RSV-mediated LRTD events is not reached^a). In addition, if participants are also enrolled in the SH, an IA (“early IA”) can also occur during the NH or SH RSV season.

The primary analysis is the analysis performed by the sponsor that addresses the primary efficacy objectives of the study. The primary analysis can be triggered in 1 of 3 ways:

- by an IA performed by the IDMC with “superiority” or “futility” as outcome;
- by a predefined number of RT-PCR-confirmed RSV-mediated LRTD events at the end of the first RSV season. The end of the first RSV season is defined as the end of the NH RSV season in case the study is performed in the NH only, and as the end of the SH RSV season in case the study is performed in both hemispheres;
- when the end of the second RSV season is reached (if applicable).

^a The cut-off of 14 RT-PCR-confirmed RSV-mediated LRTD events at the early IA analysis and the cut-off of 18 RT-PCR-confirmed RSV-mediated LRTD events at the end of the RSV season are based on modelling and simulations described in a separate modeling and simulations report.

In case the primary analysis is triggered by an IA performed by the IDMC, the primary analysis will be performed on the same database as the IDMC to guarantee consistent results.

More information on the planned analyses can be found in Section [11.12](#).

11.1. Analysis Sets

Vaccination assignment will follow the as-treated principle.

- The Full Analysis Set (FAS) will include all randomized participants with a documented vaccine administration, regardless of the occurrence of protocol deviations. The FAS is the primary safety population. The analysis of solicited and unsolicited AEs after the Day 1 vaccination will be restricted to a subset of the FAS (ie, the Safety Subset).^a The analysis of solicited and unsolicited AEs after revaccination on Day 365 (Month 12)/Day 730 (Month 24)/Day 1,095 (Month 36) will be restricted to participants of the Revaccination Subcohorts that are part of the FAS.
- The Per-protocol Immunogenicity (PPI) population will include all randomized and vaccinated participants, for whom immunogenicity data are available. Samples taken after a participant experienced a major protocol deviation expecting to impact the immunogenicity outcomes will be excluded from the PPI. The list of major protocol deviations to be excluded from the immunogenicity analysis will be specified in the Statistical Analysis Plan (SAP) or major protocol deviation criteria document which will be finalized before database lock and unblinding. The analysis of immunogenicity will focus on 2 subsets of the PPI, ie, the Immuno Subset and the Revaccination Subcohorts.

In addition, for participants who experience a natural RSV infection (based on RT-PCR, or other sources), samples taken after the natural infection will not be taken into account in the assessment of the immunogenicity.

The PPI population is the primary immunogenicity population. For key tables, sensitivity immunogenicity analyses will also be performed on the FAS, including participants for whom immunogenicity measures are available. Excluded samples might be taken into account as well in the sensitivity analysis.

- The Per-protocol Efficacy (PPE) population will include all randomized and vaccinated participants excluding participants with major protocol deviations expecting to impact the efficacy outcomes. The list of major protocol deviations to be excluded from the efficacy analysis will be specified in the SAP or major protocol deviation criteria document which will be finalized before database lock and unblinding. Any participant with an RT-PCR-confirmed RSV-mediated ARI with onset within 14 days after vaccination will be excluded from the PPE population. Participants who discontinue within 14 days after vaccination will be excluded from the PPE population as well.

The PPE population is the primary efficacy population. Sensitivity efficacy analyses will also be performed on the FAS. For exploratory efficacy analyses focusing on data from the second

^a The specification of this subset for analysis of solicited and unsolicited AEs does not preclude the investigator from reporting an AE in any participant if he/she considers the event to be of clinical relevance and/or related to the study vaccine.

RSV season only, the participants of Revaccination Subcohort A will be additionally excluded. For analyses focusing on data from the third RSV season, participants of Revaccination Subcohorts A and B will be excluded. For exploratory efficacy analyses focusing on data over 2 RSV seasons, the second RSV season data will be excluded for the participants of Revaccination Subcohort A. For analyses focusing on data over 3 RSV seasons, second and third RSV season data will be excluded for the participants of Revaccination Subcohort A, and third RSV season data will be excluded for participants of Revaccination Subcohort B. Participants who develop major protocol deviations expecting to impact the efficacy outcomes and occurring up to the considered RSV season will be **additionally** excluded from the PPE when focusing on data including the second or third RSV season.

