11.2. Sample Size Determination

11.2.1. Efficacy

Under the following assumptions:

- a VE for Case Definition #2 of 70%
- and an incidence of Case Definition #2 of 0.75% in placebo recipients during the RSV season, assuming vaccination occurs before the RSV season
- 3 primary endpoints which are nested (see Section 11.4.1)
- a 1-sided α of 5% (total: as described in Section 11.4.1.1, corrections are performed for multiple endpoints and for IAs outlined in Section 11.12)
- 10% of exclusions (due to drop-out, major protocol deviations, etc.)

Simulations performed in R show that for a NH only study, 2,750 participants per vaccination group result in 80% total power to demonstrate $VE > 0$ for Case Definition #2 at the end of the RSV season, resulting in a total sample size of 5,500 participants. The end of the first RSV season is then defined as the end of the NH RSV season.

In case recruitment is not completed in the NH (and less than 18 RT-PCR-confirmed RSV-mediated LRTD events (using Case Definition #2) are observed in the NH before opening sites in the SH), enrollment will continue in the SH. As there is the possibility to have an early IA during the NH or SH RSV season (see Section 11.12), an additional 150 participants per vaccination group is needed to have 80% total power to demonstrate $VE > 0$ for Case Definition #2 at the end of the RSV season. The end of the first RSV season is defined as the end of the SH RSV season in case the study is performed at both hemispheres. So, if recruitment is spread over 2 hemispheres, the total sample size will be 5,800 participants.

With respect to Case Definitions #1 and #3, further simulations showed that the power to obtain a significant result for any case definition, after multiplicity correction that control the type I error at 5%, tended to be similar or better than for Case Definition #2 alone, without multiplicity correction. This result was valid over a broad range of incidence and vaccine efficacies, unless the VE for the most common case definition (Case Definition #3), was $> 20\%$ lower than the VE for Case Definition #2. Case Definition #2, which incidence lies between that of Case Definition #1

and #3, was chosen as basis for the power calculations and decision rule, as more prior information was available for this case definition in the literature. Under the assumptions described above, it is expected to observe 26 cases.

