As a sensitivity analysis, the above model will be repeated based on the FAS (which also does not take into account the restriction on the onset [at least 14 days] and will count cases from vaccination on Day 1 onwards). Additional sensitivity analyses will include an exact binomial test, not taking into account the strata, based on the PPE population and the FAS. The VE (1-relative

risk) and the corresponding corrected 2-sided CI based on the exact binomial will be calculated as well.

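### Section 11.1 groups participants as treated in every analysis set, so no planned efficacy analysis, including the FAS sensitivity analyses, compares the arms as randomised (minor, free to fix)

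*Protocol*

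**What the plan says.** Section 11.1 of the protocol begins with a grouping rule, "Vaccination assignment will follow the as-treated principle", and then defines the FAS, the PPI and the PPE. The rule is not restricted to safety, and nothing elsewhere in the protocol gives efficacy a different grouping.

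Membership of the FAS is broad: "The Full Analysis Set (FAS) will include all randomized participants with a documented vaccine administration, regardless of the occurrence of protocol deviations". The section names the FAS as the primary safety population. For efficacy, "The PPE population is the primary efficacy population", and "Sensitivity efficacy analyses will also be performed on the FAS".

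Section 11.4.1.1 says what those analyses are. The exact Poisson model is run again: "As a sensitivity analysis, the above model will be repeated based on the FAS". That run drops the 14-day onset restriction and counts cases from Day 1. A simpler test is added: "Additional sensitivity analyses will include an exact binomial test, not taking into account the strata, based on the PPE population and the FAS".

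**The concern.** As-treated grouping suits safety, where the question is what follows exposure to a product. For efficacy, the protection against bias comes from comparing arms as randomised. The primary analysis already departs from that by using a per-protocol set, so the FAS analysis is where one would look for a comparison that keeps the randomised groups among everyone vaccinated.

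Under the rule as written, the FAS restores the participants whom the PPE removes, but it does not restore their randomised group if they received the other product. The reference in the FAS definition to randomised participants settles who is in the set, not the arm in which they are counted. The plan therefore contains no efficacy analysis by randomised arm.

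This is not detail left to the SAP. The protocol fixes the rule, and a SAP that follows it carries it forward. With about two dozen cases expected, it is fair to ask what one regrouped case could do.

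**Working it through.** **Inputs (Section 11.2.1).** VE 70% for Case Definition #2, so a rate ratio of 0.30; placebo incidence 0.75%; 10% exclusions; 2,750 per group (2,900 if both hemispheres recruit); one-sided total alpha 5%; 26 cases expected. Section 11.4.1.1 gives a worked example with 14, 18 and 25 events on the three case definitions, an alpha of 0.0335 per analysis and a cut-off of 0.0175.

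**Reproducing the plan's figures.**
- Expected cases = n × 0.0075 × (1 + 0.30). With 2,750 per group: 26.8 before exclusions and 24.1 after 10%. With 2,900 per group after 10%: 25.4. These bracket the stated 26.
- Power by the exact conditional binomial test with 2,475 per group, at one-sided 0.05 without multiplicity correction: 81.7%, against the stated 80%.
- Pocock alpha at information fraction 0.7: 0.0335, as stated.
- Common cut-off for three nested endpoints with 14, 18 and 25 events (correlation = square root of the event ratio): 0.0174 at a total of 0.0335, matching the stated 0.0175. The same calculation at a total of 0.05, with no interim, gives 0.0268. That second figure is a recalculation and is not in the protocol. It depends only on the event ratios, so using it with 24 or 26 cases assumes the same ratios.

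**Effect of one case changing arm.** Suppose a participant randomised to vaccine but given placebo becomes a case. As treated, the case counts under placebo; as randomised, under vaccine. The exact one-sided p is P(X ≤ x) for X ~ Binomial(n, 0.5), where x is the number of vaccine cases:

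| Total cases | As treated (vaccine:placebo) | p | As randomised | p |
|---|---|---|---|---|
| 18 | 4:14 | 0.0154 | 5:13 | 0.0481 |
| 24 | 6:18 | 0.0113 | 7:17 | 0.0320 |
| 26 | 7:19 | 0.0145 | 8:18 | 0.0378 |
| 26 (expected split) | 6:20 | 0.0047 | 7:19 | 0.0145 |

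The first three rows start on the last passing split and cross both 0.0175 and 0.0268. At 24 cases, VE (1 − case ratio) falls from 67% to 59%. The fourth row starts at the split that the design expects (26 × 0.30/1.30 = 6) and crosses neither cut-off.

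**How often this could arise.** Under the design (24.1 expected cases, VE 70%), the result lies on the last passing split with probability 14% (alpha 0.05) to 18% (alpha 0.0175). The protocol gives no dispensing-error rate. Assume 0.1% to 1% of 5,500, that is 5.5 to 55 people. Mean incidence over the two arms is (0.75% + 0.225%)/2 = 0.49%, so 0.03 to 0.27 misallocated cases are expected, or a 3% to 24% chance of at least one. If the two events are independent, the product is about 0.4% to 4%, before requiring that the case moves in the harmful direction.

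These p-values are unstratified. The planned stratified exact Poisson model with a follow-up offset would differ slightly.

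**The case against.** A reader might infer that this rule puts the proof-of-concept decision at risk. The protocol does not support that. Sections 2.2 and 11.4.1.1 decide proof of concept on the PPE; the FAS analyses are sensitivity analyses. Section 11.1 leaves the list of major deviations to the SAP or a deviation document, and that list may remove recipients of the wrong product from the PPE. A misallocated case would then leave the analysis instead of changing arm: 6:18 becomes 6:17, with p=0.0173, below both cut-offs. Only if such participants stayed in the PPE would as-treated grouping reach the formal test. The document does not settle this, and deferring the list is no fault.

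A reader might also infer that the FAS analysis cannot check the PPE at all. That too goes too far. The FAS keeps participants with protocol deviations, restores RSV infections with onset in the first 14 days and early discontinuations, and so still tests those exclusions. Only wrong-product recipients are handled differently.

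Finally, the two groupings should seldom differ. The comparison rests on a single Day 1 injection, with central randomisation through the IWRS (Section 5) and syringes labelled by participant number (Section 6). There is no adherence-driven crossover at Day 1, only dispensing error.

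All of this stands and limits the size of the point. None of it supplies an efficacy analysis by randomised arm.

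**Conclusion.** The point holds in a narrow form. Section 11.1 fixes as-treated grouping for every set, so the FAS efficacy sensitivity analyses count wrong-product recipients by vaccine received, and no planned efficacy analysis compares the arms as randomised. The effect is confined to Day 1 dispensing errors in an analysis that does not decide proof of concept, provided that wrong-product recipients are excluded from the PPE. With 24 to 26 cases, one regrouped case alters the reading only when the result lies at the boundary, not at the expected 6:20 split. How often it would matter depends on an error rate that the protocol does not give; the assumed 0.1% to 1% puts it at a few percent at most. Severity is minor: a free improvement.

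**What to change.** Replace the opening rule of Section 11.1 with one that separates the two purposes, for example: *Safety analyses group participants by the vaccine received. Efficacy analyses on the FAS group participants by randomised arm. Receipt of the wrong product on Day 1 is a major deviation that excludes the participant from the PPE.* Carry the same wording into the SAP and the deviation criteria document, if it is not already there. The cost is that wording. It needs no new data, no further participants and no change to the primary analysis model or the alpha.

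If no dispensing errors occurred, the two groupings coincide, and the study report can say so.

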* Participants in Revaccination Subcohort 1B cannot have participated in the Immuno Subset of Cohort 1. Therefore, visits from the [Schedule of Activities – Cohort 1 \(N=5,800\)](#) which pertain to the Immuno Subset only (Day 85, Day 169, and Day 533) are not included here.

Clinic Visit #	1	2	2a 	3 	4	5	
Visit Timing	Vac 1	Vac 1 +14 d	Vac 1 +28 d	End of 1 st RSV Season	Vac 1 + 365 d	End of 2 nd RSV Season	
Visit Month	0		1		12		
Visit Day	1	15 ^a	29 ^a		365 ^a		
Visit Window		+3 d	+3 d	+35 d	±2 mo	-7/+14 d	
Revaccination Subcohort 1B (N=135)							
Solicited AE recording ^t	●						
Unsolicited AE recording ^u		Continuous					
SAEs ^v		Continuous until the end of the first RSV season (or 6 months after vaccination, whichever comes later), and from revaccination on Day 730 until 6 months after revaccination ^{dd}					
AESIs ^v							
AEs and special reporting situations related to study procedures and non investigational (concomitant) Janssen products	Continuous until the end of the participant's study participation						
AEs leading to discontinuation (from study)		Continuous until the end of the participant's study participation					
Concomitant medications ^{w,x}		Continuous until the end of the participant's study participation ^z					
ARI surveillance ^{aa}		Twice per week via the eDiary from vaccination on Day 1 until the end of the first RSV season, from Day 365 until the end of the second RSV season, and from the end of the second RSV season until revaccination on Day 730					
eDiary review of solicited AEs by study staff		●					
Experience Survey				● ^{bb}			
Humoral immunity sample, mL	● 15 ^y	15 ^y			15		
Blood Draw Volumes							
Approx. daily blood draw, mL	15	15			15		
Approx. cumulative blood draw, mL	15	30	30	30	45	45	

The table continues on the next page with Visit 6 through Visit 7e.

Clinic Visit #	6	7	7a	7b	7c	7d	7e
Visit Timing	Vac 2	Vac 2 +7 d	Vac 2 +14 d	Vac 2 +28 d	Vac 2 +84 d	Vac 2 +24 we	Vac 2 +52 we/
Visit Month	24			25	27	30	36
Visit Day	730 ^a	737 ^a	744 ^a	758 ^a	814 ^a	898 ^a	1,095 ^a
Visit Window	±1 mo ^{cc}	±2 d relative to Vac 2	+3 d relative to Vac 2	+3 d relative to Vac 2	±7 d relative to Vac 2	±14 d relative to Vac 2	±1 mo relative to Vac 2
Revaccination Subcohort 1B (N=135)							
Written informed consent for participation in subcohort ^c	❶						
Pre vaccination medications	❶ ^g						
Check for seasonal influenza and SARS CoV 2 vaccination	❶ ❷	❷	❷	❷			
Physical examination ^h	❶						

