Visit Day	1	15 ^a	29 ^a		365 ^a	
Visit Window		+3 d	+3 d	+35 d	±2 mo	-7/+14 d
Revaccination Subcohort 2B (N=135)						
Contraindications to vaccination						
Vaccination	●					
30 minute post vaccination observation ^s	●					
Solicited AE recording ^u	●					
Unsolicited AE recording ^v		Continuous				
SAEs ^w		Continuous until the end of the first RSV season (or 6 months after vaccination, whichever comes later), and from revaccination on Day 730/Day 1,095 until 6 months after revaccination ^{ee}				
AESIs ^w						
AEs and special reporting situations related to study procedures and non investigational (concomitant) Janssen products		Continuous until the end of the participant's study participation				
AEs leading to discontinuation (from study)		Continuous until the end of the participant's study participation				
Concomitant medications ^{x,y}		Continuous until the end of the participant's study participation ^{aa}				
ARI surveillance ^{bb}		Twice per week via the eDiary from vaccination on Day 1 until the end of the first RSV season, from Day 365 until the end of the second RSV season, and from the end of the second RSV season until revaccination on Day 730				
eDiary review of solicited AEs by study staff		●				
Experience Survey				● ^{cc}		
Humoral immunity sample, mL	① 15 ^z	15 ^z			15	
Blood Draw Volumes						
Approx. daily blood draw, mL	15	15			15	
Approx. cumulative blood draw, mL	15	30	30	30	45	45

The table continues on the next page with Visit 6 through Visit 7d.

Clinic Visit #	6	7	7a	7b	7c	7d			
Visit Timing	Vac 2	Vac 2 +7 d	Vac 2 +14 d	Vac 2 +28 d	Vac 2 +84 d	Vac 2 +24 we			
Visit Month	24			25	27	30			
Visit Day	730 ^a	737 ^a	744 ^a	758 ^a	814 ^a	898 ^a			
Visit Window	±1 mo ^{dd}	±2 d relative to Vac 2	+3 d relative to Vac 2	+3 d relative to Vac 2	±7 d relative to Vac 2	±14 d relative to Vac 2			
Revaccination Subcohort 2B (N=135)									
Written informed consent for participation in subcohort ^c	●								
Pre vaccination medications	● ^g								
Check for seasonal influenza and SARS CoV 2 vaccination	● ²	● ²	● ²	● ²					
Physical examination ^h	●								
eDiary training and distribution ⁱ	● ^o								
Thermometer training and distribution	●								
Ruler training and distribution	●								
Verification of selected eligibility criteria	● ^q								
Contraindications to vaccination	●								
Vaccination	●								
30 minute post vaccination observation ^s	●								
Solicited AE recording ^u	●	●							

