For example: assume in a NH and SH study an IA was performed with 18 RT-PCR-confirmed RSV-mediated LRTD events observed of the expected 26: the IFs for the interim and primary analyses are 0.7 and 1, respectively. With a total α of 0.05, the α at each analysis (IA and primary analysis) will be 0.0335 using Pocock's rule. If then at the IA the total number of events are as follows: 14 events with Case Definition #1, 18 events with Case Definition #2, and 25 events with Case Definition #3, the IFs at the IA are: 0.56, 0.72, and 1. Again, using Pocock's rule, the α for each individual case definition will be 0.0175. So, proof of concept will be declared at the IA if, for any endpoint, the comparison of the number of events on vaccine compared to placebo if the p-value is <0.0175 .

For each of the 3 primary endpoints the following will be performed: an exact Poisson regression will be fitted with the event rate, defined as the number of cases over the follow-up time (offset) as dependent variable and the vaccination group and age and being at increased risk for severe RSV disease (both as stratified) as independent variables. For cases, the follow-up time is defined as the time between vaccination and the occurrence of the first event (according to the considered endpoint), for non-cases, it is the time between vaccination and the end of season visit. However, for participants that discontinued before the end of the season and had an event (according to the considered endpoint), the follow-up time is defined as the time between vaccination and the occurrence of the first event and for participants that discontinued before having an event, follow-up time is the time between vaccination and the date of last contact. Thus, all participants are included in the analysis according to their follow-up time. The exact p-value corresponding to vaccination group will be compared with the cut-off as described above.

If the p-value is below the cut-off for at least 1 of the 3 primary endpoints, proof of concept is demonstrated. The individual 2-sided CIs ($1-2 \times \text{cut-off}$) for the VE (1-relative risk rate), measured by each of the 3 endpoints, will be calculated from the regression model described above.

The primary analysis will be performed on the PPE population, which will take cases into account with an onset at least 14 days after vaccination.

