For exploratory endpoints over 2 seasons (Season 1 and Season 2), the follow-up time is defined as the time between the Day 1 vaccination and the occurrence of the first event (according to the considered endpoint) in the first 2 seasons, for non-cases, it is the time between the Day 1 vaccination and the end of the second season visit. However, for participants that discontinued before the end of the second season and had an event (according to the considered endpoint), the follow-up time is defined as the time between the Day 1 vaccination and the occurrence of the first event and for participants that discontinued before having an event, follow-up time is the time between the Day 1 vaccination and the date of last contact. For Revaccination Subcohort A participants, only the first season is taken into account: for cases during the first season, the follow-up time is the time between the Day 1 vaccination and the occurrence of the first event (according to the considered endpoint), for non-cases it is the time between the Day 1 vaccination and end of first season visit.

For exploratory endpoints over 3 seasons (Season 1, 2 and 3), the follow-up time is defined similar as for endpoints over 2 seasons, but data up to the end of the third season are taken into account (instead only data up to the end of the second RSV season). For Revaccination Subcohort A participants, only the first season is taken into account and follow-up time is defined similar as explained above. For Revaccination Subcohort B participants only the first 2 seasons are taken into account: for cases during the first 2 seasons, the follow-up time is the time between the Day 1 vaccination and the occurrence of the first event (according to the considered endpoint), for non-cases it is the time between the Day 1 vaccination and the end of second season visit.

For continuous endpoints, actual values and changes from baseline (if meaningful) will be summarized descriptively. Categorical endpoints will be tabulated.

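### The exploratory multi-season efficacy analyses discard cases and follow-up that precede a later deviation or, in Subcohort B, the revaccination

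*Protocol*

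**What the plan says.** **Deviations.** Section 11.1 of the protocol, repeated in the synopsis, states for the PPE: "Participants who develop major protocol deviations expecting to impact the efficacy outcomes and occurring up to the considered RSV season will be" additionally excluded when the analysis includes second- or third-season data. The list of qualifying deviations is left to the SAP or a separate criteria document. The unit of exclusion, the participant, is fixed in the protocol.

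**How the same section treats similar situations.** For the PPI, the rule is dated: "Samples taken after a participant experienced a major protocol deviation expecting to impact the immunogenicity outcomes will be excluded from the PPI". For the revaccination subcohorts in the cumulative analyses, only later-season data go; over 3 seasons, "third RSV season data will be excluded for participants of Revaccination Subcohort B".

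**Model.** Section 11.4.1.1 uses a Poisson regression with follow-up time as offset and concludes: "Thus, all participants are included in the analysis according to their follow-up time". Section 11.4.3.1 carries this model over to the exploratory VE endpoints.

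**Subcohort B over 3 seasons.** Section 11.4.3.1 says: "For Revaccination Subcohort B participants only the first 2 seasons are taken into account", and "for non-cases it is the time between the Day 1 vaccination and the end of second season visit". For participants outside Subcohorts A and B, follow-up runs from Day 1 to the end of the third season without a stated break.

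**Surveillance.** The Schedules of Activities for Subcohorts 1B and 2B continue twice-weekly ARI surveillance "from the end of the second RSV season until revaccination on Day 730". At that time site and participant are still blinded to the Day 1 vaccination.

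**The concern.** Whether an observed case enters the cumulative analysis depends on what happens to the participant afterwards. A valid Season 1 case counts in the Season 1 analysis, then disappears from the over-2- and over-3-season analyses if a major deviation is recorded in a later year. A Subcohort B participant's RSV illness in summer or autumn 2021 is collected under the same surveillance as everyone else's, then left out because that participant was later revaccinated.

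This is selection on post-baseline events. At stake are the precision of the durability estimates and, if the selection works differently in the two groups, their validity. With only about 26 Case Definition #2 cases expected in the first season, single cases carry weight. Section 11.12 also ties continuation into a third season to an apparent durability trend.

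**Working it through.** **1. The rules side by side**

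| Situation | What is dropped | Dated? |
|---|---|---|
| PPI, major deviation (11.1) | samples after it | yes |
| Subcohorts A and B, cumulative PPE (11.1) | later-season data | yes |
| PPE with Season 2 or 3 data, major deviation (11.1) | the whole participant | no |
| Subcohort B over 3 seasons (11.4.3.1) | everything after the Season 2 visit | yes, but earlier than the switch |

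The text does not say whether a deviation during the considered season counts. The point holds either way: a deviation between Seasons 1 and 2 already removes a Season 1 case from the over-2-season analysis. In a single-season analysis the rule can cost only the pre-deviation part of that season.

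The Subcohort B cut matters only over 3 seasons. The Season 3 analysis starts at Day 730, and the 2-season analysis keeps Subcohort B in full. Subcohort A loses nothing this way, because no surveillance is planned between the end of Season 1 and Day 365.

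**2. The plan's own figure (Section 11.2.1)**

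Inputs: placebo incidence 0.75%, VE 70%, 10% exclusions. Expected cases = n × 0.9 × 0.0075 × (1 + 0.30).
- n = 2,750 per group: 18.56 + 5.57 = 24.1
- n = 2,900 per group: 19.57 + 5.87 = 25.4 (20 + 6 = 26 with each group rounded up)

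The stated 26 is reproduced to within 2 cases.

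**3. Season 1 cases lost through later deviations**

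The protocol gives no rate of later deviations. Assume a fraction d from 1% to 10%, unrelated to being a case. Cases lost = d × expected cases.
- d = 1%: 0.01 × 24.1 = 0.24
- d = 10%: 0.10 × 25.4 = 2.5

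If two full seasons at the same incidence precede the deviation (also assumed), these double to about 0.5 and 5.

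**4. Subcohort B gap**

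Inputs: 135 per group (270 in all), end of Season 2 on 17 May 2021, Day 730 visit no later than the end of November 2021.
- Longest gap: 17 May to 30 November = 197 days; 270 × 197 / 365.25 = 146 person-years.
- Shorter gap, assuming revaccination on 1 August: 76 days; 270 × 76 / 365.25 = 56 person-years.

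The Season 2 visit window (−7/+14 days) shifts these slightly.

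Cases in the gap = f × 135 × 0.0075 × 1.3, where f is the inter-season risk as a fraction of the in-season risk (assumed 0 to 1). This gives 0 to 1.3.

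**5. When VE is biased**

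With equal person-time, VE after loss = 1 − [V(1 − fv)] / [P(1 − fp)], where V and P are the vaccine and placebo cases and fv and fp the fractions lost. If fv = fp the factors cancel. With 20 placebo and 6 vaccine cases and 10% lost from each, 1 − 5.4/18 = 70%, the same as 1 − 6/20.

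**The case against.** The case for leaving the text alone has real force.

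- **The analyses are exploratory.** The primary hypothesis, its alpha and the first-season analysis are untouched. This stands, and it limits the severity.
- **The FAS sensitivity analysis keeps deviators.** A case dropped from the PPE remains there, so a discrepancy would show. This stands in part. As described in Section 11.4.1.1, the FAS analysis also lifts the 14-day onset restriction, so it does not isolate the effect of the deviation rule. It also does nothing for Subcohort B, whose follow-up rule is not confined to the PPE.
- **Whole-participant exclusion is the general PPE convention, and the PPI concerns repeated samples.** It is true that this is no contradiction. But a rate model with a follow-up offset handles censoring directly, so the convention gains little here.
- **The Subcohort B cut is ordinary administrative censoring.** Event and time stop together, identically in both groups, at the point when Subcohort B is identified. The longest gap is about 1% of total follow-up (146 / (5,800 × 2.6) ≈ 1.0%, before drop-out). This stands as to bias. It does not justify discarding pre-switch data already collected under blinding at site and participant level.
- **The protocol does not say outright that inter-season cases count for the other participants.** Section 11.4.3 speaks of 2 or 3 seasons, while the follow-up rule in Section 11.4.3.1 runs without a break. This also stands, and the fix should settle it.

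**Conclusion.** The point holds as a minor one. As written, the cumulative PPE analyses lose cases and person-time that precede a deviation, and the over-3-season analysis loses Subcohort B's follow-up between the Season 2 visit and Day 730. The likely size is about 0.24 to 2.5 Season 1 cases, resting on an assumed 1% to 10% later-deviation rate, plus 0 to 1.3 cases and up to about 146 person-years for Subcohort B, resting on 270 participants and the latest permitted revaccination date. Whether any case is actually lost cannot be known from the protocol.

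A reader might infer that the rule pulls VE towards zero, because respiratory illness could lead to treatment that counts as a deviation and placebo has more cases. Losing 2 of 20 placebo cases and none of 6 vaccine cases would indeed give 1 − 6/18 = 66.7% instead of 70%. The document does not support that direction. More cases in one arm is not enough; the fraction lost must differ. Section 8 prohibits immunomodulating agents, but for chronic corticosteroids it requires documentation and contact with the sponsor, and the list of major deviations is not in the protocol. Differential loss is possible but not shown.

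Nor do Sections 11.1 and 11.4.3.1 contradict each other on Subcohort B: excluding third-season data and counting two seasons are compatible. They leave the interval between the seasons unaddressed or discarded.

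**What to change.** In Sections 11.1 and 11.4.3.1 and the matching synopsis text, for analyses covering more than one season:

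- Censor each participant at the date of the first post-baseline major deviation and keep events with onset before it. Deviations present at Day 1 still exclude the participant.
- For over-3-season endpoints, censor Subcohort B at the Day 730 revaccination instead of the end-of-Season-2 visit.
- State whether cases between seasons count, and apply the same rule to all participants.

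The cost is wording and programming; no new assessments are needed, as surveillance and revaccination dates are already collected. The downside is that the cumulative PPE is no longer a fixed set of participants, so tables should report the number censored and the person-time by arm.
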